### 5 RESULTS

#### 5.1 POSTOPERATIVE PAIN INTENSITY

The analysis demonstrated significant main effects of treatment ( $F_{(1,16)} = 5.063$ ,  $p = 0.039$ ) and time ( $F_{(7,112)} = 6.254$ ,  $p < 0.001$ ) on postoperative pain intensity (Table 1). Overall, pain scores were higher in Group A than in Group B ( $2.0 \pm 1.2$  vs.  $1.3 \pm 1.1$ ;  $F_{(1,16)} = 5.063$ ,  $p = 0.039$ ).

[figure not shown]

[figure not shown]
Table 1: Average pain levels on every post-operative day for each group. (\*) indicates statistical differences between control and test groups.

In Group A, pain intensity was significantly higher on postoperative days 1 ( $3.59 \pm 0.59$ ;  $p = 0.014$ ) and 3 ( $3.24 \pm 0.55$ ;  $p = 0.005$ ) compared with day 0 ( $1.35 \pm 0.54$ ). No significant differences were observed between day 0 and the remaining postoperative time points ( $p > 0.05$ ).

[figure not shown]
On the test side (Group B), no significant differences in pain intensity were observed between day 0 and any postoperative evaluation ( $p > 0.05$ ), suggesting that cryotherapy effectively prevented postoperative pain exacerbation.

A significant interaction between treatment and time was also observed ( $F_{(7,112)} = 2.689$ ,  $p = 0.013$ ). Pain intensity was higher on postoperative day 1 (Group A:  $3.59 \pm 0.59$  vs. Group B:  $2.12 \pm 0.42$ ;  $p = 0.017$ ) and day 3 (Group A:  $3.24 \pm 0.55$  vs. Group B:  $1.29 \pm 0.33$ ;  $p = 0.007$ ) in the control group compared with the cryotherapy group.

Postoperative pain was absent in 29.4% of control cases and 44.1% of cryotherapy cases. Mild pain was reported by 50.0% of participants in Group A and 47.8% in Group B, whereas moderate pain occurred in 16.9% and 7.4% of cases, respectively. Severe pain was reported by 3.7% of control cases and 0.7% of cryotherapy cases (Graphics 1 and 2).

Graphic 1: Prevalence of reports of moderate to severe pain (4-10 in visual analogic scale) in the total number of reports of pain (1-10 in visual analogic scale) in the control group after day 2 (last day of analgesic medication).

12

Graphic 2: Prevalence of reports of moderate to severe pain (4-10 in visual analogic scale) in the total number of reports of pain (1-10 in visual analogic scale) in the test group after day 2 (last day of analgesic medication).

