## 6 DISCUSSION

Cryotherapy was effective in reducing both the intensity and duration of postoperative pain episodes, as well as shortening the period of mouth opening limitation. Additionally, its use in the postoperative period resulted in a reduced need for rescue medication and a greater patient-perceived improvement over time. These findings support the consolidation of a cryotherapy protocol, contributing to a more predictable postoperative course and improving the management of postoperative complications.

As shown in Table 1, differences in mean pain scores during the first 72 postoperative hours (from day 0 to the end of day 2) appear to be related to the lack of consolidation of the inflammatory response under pharmacological analgesia alone. Pain modulation was only stabilized after postoperative day 3 in both groups, as also reported by Sukegawa et al. However, cryotherapy demonstrated a

beneficial synergistic effect when combined with analgesic medication, resulting in lower pain scores during this critical period. In contrast, analgesic therapy alone was insufficient to adequately control pain in the control group, which exhibited two distinct peaks in pain intensity at 24 and 72 hours postoperatively.

The benefit of cryotherapy for the test group was particularly evident between postoperative days 2 (the last day of analgesic medication) and 3 (the first day without medication). During this transition, pain levels increased in the control group and remained consistently higher than those observed in Group B, even during the consolidation phase of the inflammatory response. These findings suggest that the greater differences in pain intensity are directly associated with the absence of cryotherapy in the control group, despite the use of analgesics.

Pain severity distribution over the seven postoperative days further reinforced these findings (Graphics 1 and 2). Proportionally, extractions performed without cryotherapy were associated with a significantly higher likelihood of moderate-to-severe pain. From a clinical perspective, the absence of cryotherapy increased the probability of requiring rescue medication. This observation is particularly relevant for patients with systemic diseases who already require complex pharmacological regimens, increasing the risk of drug interactions, as well as for individuals susceptible to medication dependence, for whom minimizing drug exposure is essential.

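### As captioned, Graphics 1 and 2 show severity among painful reports after day 2, so they do not support the Discussion's seven-day statement on how often moderate-to-severe pain occurs

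*Combined protocol and SAP*

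**What the plan says.** Three places describe the same pair of graphics.

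- **Captions, section 5.1.** The numerator is reports scored 4-10. For Graphic 1 the denominator and period are "in the total number of reports of pain (1-10 in visual analogic scale) in the control group after day 2"; for Graphic 2 they are "in the total number of reports of pain (1-10 in visual analogic scale) in the test group after day 2". Zero scores and days 0-2 are outside both.
- **Results text, section 5.1.** A four-category distribution is given, starting with "Postoperative pain was absent in 29.4% of control cases and 44.1% of cryotherapy cases" and continuing through mild (50.0% and 47.8%), moderate (16.9% and 7.4%) and severe (3.7% and 0.7%). It also points to Graphics 1 and 2.
- **Section 6, Discussion.** "Pain severity distribution over the seven postoperative days further reinforced these findings" cites Graphics 1 and 2. The next sentence says that "extractions performed without cryotherapy were associated with a significantly higher likelihood of moderate-to-severe pain". It gives no percentage, ratio, interval or p-value.

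Section 4.8 plans the pain categories as a descriptive frequency distribution and names no test for them.

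**The concern.** The captions and the two citations cannot all be right. A figure limited to scores 1-10 cannot display a no-pain share, and a figure limited to the days after day 2 is not a seven-day distribution.

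The difference affects what may be concluded. Whether a report is painful at all is itself a post-treatment outcome. A share taken among painful reports answers the question of how bad pain was when there was pain. The Discussion makes a statement about extractions: how likely moderate-to-severe pain is afterwards. That needs every scheduled report in the denominator.

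The window matters too. It leaves out day 1, the highest control mean that section 5.1 reports (3.59 against 2.12) and one of the two days on which that section reports a difference between sides. A reader told that the graphics cover seven days would think day 1 is included. Section 6 then moves from this sentence to the probability of needing rescue medication, and later cites Graphic 2 again in its quality-of-life paragraph.

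**Working it through.** **Inputs.** 17 patients analysed, so 17 control and 17 test sites (section 4.4). Pain was scored daily to day 7 (section 4.7). The time effect has 7 and 112 degrees of freedom (section 5.1): 8 - 1 = 7 and 16 × 7 = 112, so there are eight time points, days 0-7. The category percentages are those in section 5.1.

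**Step 1: which reports do the printed percentages describe?** Scheduled reports per side over days 0-7: 17 × 8 = 136.

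| Category | Control | Cryotherapy |
|---|---|---|
| None | 40/136 = 29.4% | 60/136 = 44.1% |
| Mild | 68/136 = 50.0% | 65/136 = 47.8% |
| Moderate | 23/136 = 16.9% | 10/136 = 7.4% |
| Severe | 5/136 = 3.7% | 1/136 = 0.7% |

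All eight percentages are reproduced to one decimal. Of the denominators tried (17, 34, 68, 85, 102, 119, 136), only 136 does this. For example, 50.0% is impossible with 85 reports (days 3-7: 42/85 = 49.4%, 43/85 = 50.6%) or with 119 (days 1-7: 59/119 = 49.6%, 60/119 = 50.4%). The Results text therefore describes all reports from day 0 to day 7, zeros included, which is not what the captions describe.

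**Step 2: what does the denominator do?** Moderate plus severe: control 23 + 5 = 28, cryotherapy 10 + 1 = 11. Painful reports: control 136 - 40 = 96 (70.6%), cryotherapy 136 - 60 = 76 (55.9%).

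| Days 0-7 | Control | Cryotherapy | Difference | Ratio |
|---|---|---|---|---|
| All reports | 28/136 = 20.6% | 11/136 = 8.1% | 12.5 points | 2.55 |
| Painful reports only | 28/96 = 29.2% | 11/76 = 14.5% | 14.7 points | 2.02 |

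The two ratios are linked by the share of painful reports: 2.02 × (96/76) = 2.02 × 1.26 = 2.55. The factor 1.26 is the part of the contrast that conditioning on pain removes.

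**Step 3: the captioned window.** Reading it as days 3-7, the full denominator is 17 × 5 = 85 per side. The text gives no counts for those days and the graphics are not reproduced, so the plotted values cannot be recomputed.

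**Step 4: can the word *significantly* be supported?** No test of the categories is reported. As an illustration over all reports, z = (pA - pB) / √[p(1 - p)(1/136 + 1/136) × D], with p = 39/272 = 0.143 and D = 1 + (8 - 1) × ICC. The documents give no ICC, so a range is assumed.

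| Assumed ICC | D | z | p |
|---|---|---|---|
| 0 (reports independent) | 1.0 | 2.94 | 0.003 |
| 0.1 | 1.7 | 2.26 | 0.024 |
| 0.2 | 2.4 | 1.90 | 0.058 |
| 0.5 | 4.5 | 1.39 | 0.17 |
| 1 | 8.0 | 1.04 | 0.30 |

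This ignores the pairing of the two sides within a patient, so it is not a substitute for the proper analysis. It shows only that the answer depends on how repeated reports from 17 patients are handled.

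**The case against.** The strongest reply is that this is a labelling slip. Section 5.1 already prints a distribution over days 0-7 on a fixed denominator, and that distribution supports the Discussion sentence by simple addition. The captions state their window openly, and it has a purpose: they tie it to the end of the standard analgesic, and section 5.1 goes on to look at rescue use after that point. Day 3, the larger of the two reported mean differences (3.24 against 1.29), lies inside it. Since the graphics cannot be seen here, the captions rather than the plots may be at fault.

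Most of this stands, and it rules out several stronger readings that a reader might infer:

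- *The Discussion's likelihood was calculated on the painful-report denominator.* Section 6 prints no figure, so this cannot be shown.
- *The benefit is exaggerated.* Over days 0-7 the painful-report ratio is the smaller one (2.0 against 2.5). Only the absolute difference is slightly larger (14.7 against 12.5 points).
- *The contrast might merely reflect fewer mild reports.* Over days 0-7, mild reports hardly differ (68 and 65), while moderate-to-severe reports fall from 28 to 11.
- *The split-mouth pairing is lost.* The categories were planned as descriptive, and the within-patient comparison of pain scores is the repeated-measures ANOVA, which the graphics do not touch.

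What the reply does not remove is that the evidence cited for a frequency statement is, by its own caption, a different quantity over a different period. It also leaves *significantly* without a reported test.

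**Conclusion.** The point holds as a mismatch between a claim and its cited evidence. As captioned, the graphics show severity among painful reports after day 2, with a denominator that depends on treatment. They do not support a seven-day statement on the likelihood of moderate-to-severe pain, and they cannot be the source of a distribution that includes no pain. The direction over days 0-7 is unaffected: 20.6% against 8.1% of all reports, ratio 2.5.

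This rests on three assumptions: that each side contributed all 136 scheduled reports, which the exact match of eight percentages supports; that the 4-10 range in the captions equals moderate plus severe in section 4.7, where moderate starts at 3.1, which is so if scores were whole numbers; and that the period after day 2 means days 3-7. For that window neither size nor direction can be checked from the text.

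The change is worth making because it alters the plotted proportions and what they mean. It does not overturn the pain result.

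**What to change.** 1. Redraw Graphics 1 and 2 with every scheduled report as denominator: 136 per side for days 0-7, or 85 per side for a window named as days 3-7. If the captioned version is kept, label it severity among painful reports after day 2 and do not cite it as a likelihood.
2. Align the citations in sections 5.1 and 6 with whichever version is used, stating period and denominator in both places. The Results text covers eight diary days (0-7), so the Discussion should say so.
3. Rest the likelihood sentence on 28/136 (20.6%) against 11/136 (8.1%) over days 0-7.
4. Delete *significantly*, or support it with a paired analysis clustered on the 17 patients and described as an addition to the descriptive plan in section 4.8.

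The cost is two redrawn or relabelled figures, a few edited sentences and, if the significance claim is kept, one extra analysis. No new data are needed.

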#### **4.4 SAMPLE**

The sample selection consisted on patients referred to the Federal University of Rio Grande do Sul's Dentistry School. The selected patients require bilateral extraction of lower third molars under local anesthesia in two different surgical times. There will be no change to the routine care for patients volunteering in the study. The surgical procedures will be performed by the research team responsible for this study. Participants of both sexes, aged 18 to 50 years, were included in the study if they presented an indication for bilateral surgical removal of mandibular third molars in similar positions according to Pell and Gregory classification. Additional inclusion criteria comprised the absence of systemic comorbidities, local conditions free of inflammatory or infectious processes, no history of allergy to the prescribed medications, and no recent or chronic use of antibiotics, anti-inflammatory drugs, corticosteroids, or analgesics. Participants were excluded from the study if they used medications other than those prescribed by the surgeon, failed to provide the required data, belonged to Group A (control) but used postoperative ice packs, or belonged to Group B (test) and did not use ice packs as instructed by the researchers. There were three dropouts due to noncompliance with postoperative recommendations and the use of non-prescribed medication, resulting in 34 procedures performed in 17 patients.

Postoperative consultations were conducted for follow-up, suture removal, and the evaluation and treatment of any potential postoperative complications.

The selection of the control group and experimental groups were determined by a simple randomization in the immediate postoperative period. One surgical site didn't receive cryotherapy (GA), while the other site received cryotherapy with ice (GB).

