#### 4.8 STATISTICAL ANALYSIS

Data normality was assessed using the Kolmogorov–Smirnov test. Parametric analyses were applied to compare groups (control side vs. test side) and postoperative time points (from day 0 to day 7). Continuous variables, including pain intensity (VAS scores), maximum mouth opening (mm), and facial edema (mm), were expressed as means  $\pm$  standard deviation (SD).

A two-way repeated-measures analysis of variance (ANOVA), followed by Fisher's least significant difference (LSD) post hoc test, was used to evaluate the main effects of time and treatment, as well as their interaction, for pain intensity, trismus, and edema. Pain reports were also qualitatively analyzed based on the frequency distribution of pain categories (no pain, mild pain, moderate pain, and severe pain) for both groups.

Associations between pain intensity and trismus or edema were assessed using Pearson's correlation coefficient. Trismus and edema were additionally evaluated using the formulas (Baseline – Postoperative) and (Postoperative – Baseline), respectively. Qualitative data related to quality of life were presented as percentages.

All statistical analyses were performed using SPSS software (version 20.0; IBM Corp., Armonk, NY, USA). Statistical significance was set at  $P < 0.05$ .

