## 5.2 TRISMUS

Cryotherapy did not significantly affect maximum mouth opening during the postoperative period ( $F_{(1,16)} = 0.006$ ,  $p = 0.93$ ). However, a significant effect of time ( $F_{(2,32)} = 45.410$ ,  $p < 0.001$ ) and a significant interaction between treatment and time ( $F_{(2,32)} = 4.703$ ,  $p = 0.016$ ) were observed.

Mouth opening decreased on postoperative day 2 compared with baseline in both the control group ( $43.8 \pm 8.9$  vs.  $30.1 \pm 12.2$ ;  $p < 0.001$ ) and the cryotherapy group ( $39.3 \pm 8.8$  vs.  $31.4 \pm 7.9$ ;  $p < 0.01$ ). In Group A, mouth opening remained significantly reduced on postoperative day 7 compared with baseline ( $43.8 \pm 8.9$  vs.  $37.8 \pm 13.6$ ;  $p = 0.005$ ). In contrast, Group B showed recovery of mouth opening by day 7, with values comparable to baseline ( $39.3 \pm 8.8$  vs.  $40.5 \pm 8.5$ ;  $p = 0.43$ ) (Table 2).

[figure not shown]

Table 2: Average of maximal mouth opening values on days 0, 2 and 7 post-op.

Correlation analysis revealed no significant association between pain intensity

and trismus in Group B on postoperative days 2 ( $r = 0.15$ ,  $p = 0.54$ ) or 7 ( $r = 0.11$ ,  $p = 0.66$ ). In contrast, a significant positive correlation was observed in Group A on postoperative day 7 ( $r = 0.62$ ,  $p = 0.005$ ), indicating that greater pain intensity was associated with increased mouth opening restriction. No correlation was found on postoperative day 2 in Group A ( $r = 0.30$ ,  $p = 0.23$ ) (Table 3).

[figure not shown]

Table 3: Correlation between pain and trismus for control group.

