A strong association was also observed between higher pain intensity reports and increased requests for rescue medication in the control group. These results indicate that failure to use cryotherapy may increase reliance on pharmacological interventions to manage postoperative discomfort, which could otherwise be mitigated through a simple and low-cost intervention such as ice pack application for 30 minutes over a 12-hour period. Therefore, the proposed cryotherapy protocol can be considered a safe and effective approach that enhances postoperative predictability, facilitates complication control, and promotes greater patient engagement in self-care.

Trismus represents a multifactorial postoperative response influenced by surgical trauma, including osteotomy, extracellular fluid extravasation, tissue hemorrhage, and muscle fiber incision. Given the simultaneous occurrence of these factors, significant benefits of cryotherapy are not expected before consolidation of the inflammatory response, which explains the absence of intergroup differences during the first 72 postoperative hours. However, when comparing immediate postoperative measurements with those obtained on postoperative day 7, the control

group exhibited significantly greater mouth opening limitation (Table 2), indicating a longer duration of trismus. This finding is supported by the statistically significant correlation between pain intensity and trismus observed exclusively in the control group (Table 3), suggesting that higher pain levels are associated with prolonged mouth opening restriction. These results were further corroborated by the quality-of-life questionnaire, which revealed greater difficulty in mouth opening among control participants.

Edema did not show statistically significant differences between groups (Table 4), consistent with previous reports. It is hypothesized that superficial ice application may be insufficient to significantly reduce edema due to its limited penetration into deeper muscular and facial tissue planes, thereby restricting its vasoconstrictive effects.

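### The claim that cryotherapy's effect on mouth opening is absent early and present by day 7 is not supported: no between-side test is printed at either visit, and the printed means do not distinguish day 2 from day 7

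*Combined protocol and SAP*

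**What the plan says.** Section 4.8 plans a two-way repeated-measures ANOVA, "followed by Fisher's least significant difference (LSD) post hoc test", for pain, trismus and edema. It adds a change score: "Trismus and edema were additionally evaluated using the formulas (Baseline – Postoperative) and (Postoperative – Baseline), respectively".

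Section 5.2 reports no treatment main effect ("Cryotherapy did not significantly affect maximum mouth opening during the postoperative period", F(1,16) = 0.006, p = 0.93) and a treatment-by-time interaction of F(2,32) = 4.703, p = 0.016. The visit-level p-values there are all within side, against baseline:
- Day 2: "Mouth opening decreased on postoperative day 2 compared with baseline in both the control group" and in the cryotherapy group (p < 0.001 and p < 0.01).
- Day 7: control still reduced (p = 0.005), cryotherapy not (p = 0.43).

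The Discussion turns this into a time course. It says no benefit is to be expected until the inflammatory reaction has settled, "which explains the absence of intergroup differences during the first 72 postoperative hours". It then says the control side was significantly more restricted "when comparing immediate postoperative measurements with those obtained on postoperative day 7".

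**The concern.** The early statement is about a difference between sides. The day-7 statement rests on each side's change from its own starting value. A significant fall on one side beside a non-significant one on the other does not test the difference between sides, and no such test is printed for either visit. The contrast between the two visits is therefore drawn without any quantity measured the same way at both.

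The report tells clinicians when the benefit appears and offers a mechanism for the timing. If the data cannot separate day 2 from day 7, the mechanism explains a pattern that has not been shown. The Conclusion's claim of a shorter period of limited opening draws on the same within-side results.

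**Working it through.** **Inputs.** Section 5.2 gives mean ± SD opening in mm:

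| | Day 0 | Day 2 | Day 7 |
|---|---|---|---|
| Control (A) | 43.8 ± 8.9 | 30.1 ± 12.2 | 37.8 ± 13.6 |
| Cryotherapy (B) | 39.3 ± 8.8 | 31.4 ± 7.9 | 40.5 ± 8.5 |
| B − A | −4.5 | +1.3 | +2.7 |

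The number of pairs is 17 (section 4.4: "resulting in 34 procedures performed in 17 patients"). The level is 5% (section 4.8); sidedness is not stated, so two-sided is assumed.

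**Step 1, reproduce the printed tests.** The upper tail of F(2,32) at 4.703 is p = 0.0162, against the printed 0.016. F(1,16) = 0.006 gives p = 0.939, which fits the printed 0.93 if truncated.

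**Step 2, raw opening.** SE = √[(s_A² + s_B² − 2·r·s_A·s_B)/17], where r is the unstated within-patient correlation, varied from 0 to 0.9.
- Day 2: 1.3 mm; SE 3.53 to 1.49; p about 0.72 to 0.40.
- Day 7: 2.7 mm; SE 3.89 to 1.70; p about 0.50 to 0.13.

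Neither is distinguishable from zero.

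**Step 3, change from day 0.**
- Day 2: A lost 43.8 − 30.1 = 13.7 and B lost 39.3 − 31.4 = 7.9, a difference of 5.8 mm.
- Day 7: A lost 43.8 − 37.8 = 6.0 and B gained 40.5 − 39.3 = 1.2, a difference of 7.2 mm.

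The error can be recovered from the printed interaction. The B − A differences have mean −0.167 and sum of squares about it of 29.15.
- MS(interaction) = (17/2) × 29.15/2 = 123.9
- MSE = 123.9/4.703 = 26.3
- SE of a between-visit change in the side difference = √(4 × 26.3/17) = 2.49 mm, on 32 df

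This gives:
- Day 2: 5.8 mm, 95% CI 0.7 to 10.9, p = 0.026.
- Day 7: 7.2 mm, 95% CI 2.1 to 12.3, p = 0.007.

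On 16 df the p-values are 0.033 and 0.011.

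**Step 4, day 2 versus day 7.** The baseline cancels, so both scales give the same growth: 2.7 − 1.3 = 7.2 − 5.8 = 1.4 mm. With SE 2.49, t = 0.56, p = 0.58, 95% CI −3.7 to 6.5. On 16 df, p is again 0.58.

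**Step 5, where the interaction comes from.**
- Day 0 versus the mean of days 2 and 7: −4.5 − (1.3 + 2.7)/2 = −6.5, contributing 6.5² × 2/3 = 28.17 (96.6% of 29.15).
- Day 2 versus day 7: 1.4²/2 = 0.98 (3.4%), which is F = 2 × 4.703 × 0.0336 = 0.32.

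**Step 6, the part played by the day-0 gap.** It is 4.5/5.8 = 78% of the day-2 change effect and 4.5/7.2 = 62.5% of the day-7 one. Setting the gap to zero (differences 0, 1.3, 2.7) gives a sum of squares of 3.65. At the same MSE the interaction F is then (17/2 × 3.65/2)/26.3 = 0.6, and the day 2 versus day 7 share is 0.98/3.65 = 27%. The 96.6% is therefore largely a statement about day 0.

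**The case against.** The best defence is that section 5.2 uses one yardstick throughout, within-side change from baseline: both sides reduced on day 2, only the control side on day 7. A reader might infer that the Discussion used raw values for day 2 and change scores for day 7. The text does not document this. The wording about differences between sides fits raw opening, but it also fits within-side significance read as a group comparison. Table 2 is not visible here and may mark comparisons that the text omits. This limits what can be said about how the authors reached the claim. It does not supply the missing test, and the text prints none.

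Two stronger readings are also tempting, and the documents support neither.
- **The effect is practically the same at both visits.** In raw opening 2.7 mm is about double 1.3 mm, and the interval for the growth reaches 6.5 mm, nearly the whole 7.2 mm day-7 change effect. The data fail to distinguish the visits; they do not show equality.
- **Ice already helped on day 2, by 5.8 mm with p = 0.026.** Most of that figure is the day-0 gap between the two sides of the same 17 patients. In raw opening the day-2 difference is 1.3 mm, so an absence of detectable difference on day 2 is itself compatible with the printed means.

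It is also fair to say that the late-onset explanation is confined to the Discussion. The abstract and Conclusion do not repeat it, and section 5.2 openly reports the null main effect.

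**Conclusion.** The concern holds as a point about timing. The growth in the between-side difference from day 2 to day 7 is 1.4 mm (95% CI about −3.7 to 6.5, p about 0.58) on either scale, so a late-only effect and its biological explanation are unsupported. The interaction p = 0.016 does not rescue them: almost all of it is day 0 against the postoperative visits. For the same reason it does not by itself show a benefit free of baseline imbalance.

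The interval assumes sphericity, a pooled ANOVA error, 17 complete pairs and two-sided tests. The conclusion is not fragile. On 16 df, 1.4 mm would reach 5% only if the patient-level SD of the double difference were below about 2.7 mm (1.4/2.12 × √17). The printed F implies about 10.3 mm (2.49 × √17).

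What day 0 represents is unsettled. Section 4.5 describes one measurement before the first operation, used as the reference for both procedures; a single shared value could not produce two day-0 means 4.5 mm apart. Section 4.7 lists day 0 as the day of surgery, and the Discussion calls the starting value postoperative. The Discussion also counts the first 72 hours from day 0, so the largest raw side difference of the three visits lies inside the window said to show none. The change-score figures depend on how this is resolved.

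**What to change.** - Report the paired between-side difference in mouth opening at day 2 and at day 7, with 95% CIs, on one scale stated in section 4.8. Adjustment for day-0 opening is preferable, with raw and change-score results alongside. A change score alone could present the day-0 gap as an early benefit.
- Report the day 2 versus day 7 difference between those two effects, with its CI.
- Reconcile sections 4.5, 4.7 and 6 on whether day 0 is preoperative or postoperative, and whether it was measured once or before each procedure.
- In the Discussion, withdraw the biological explanation for a late-only effect. State that the data do not show the effect differing between day 2 and day 7, and that a between-side benefit on mouth opening depends on how the day-0 gap is handled. Word the Conclusion's claim about the duration of limited opening to match.

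The cost is a few contrasts and one covariate-adjusted analysis on data already held, a check of the day-0 records, and a rewritten paragraph. No new data are needed.
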